4.4. Type of Study: Randomized Controlled Trial

The simple randomization method will be used in this study, and volunteers will be divided into study and control groups at random and with equal probability, taking into account the inclusion and exclusion criteria. For simple randomization, block randomization method will be used.

4.5. Required Manpower for Research:

[name] [name] and [name]. [name] will diagnose patients and direct them for research. The first and second evaluations were blinded by [name]. [name] will be made Ayres Sensory Integration Therapy be implemented by [name]. [name] has a Ayres Sensory Integration Therapy Practitioner Certificate.

4.6. Data Collection Tools of the Research:

Sociodemographic Information Form

Participants' age, gender, time of diagnosis, number of siblings, parental education and employment status, etc. sociodemographic information form which contains the information will be used.

Sensory Profile (SP)

The Sensory Profile (SP) is a family-reported scale that provides data on children's reactions to sensory events in daily life, how sensory behaviors can contribute to performance in daily life, and what difficulties they cause in performance. It consists of 125 questions that can be applied between the ages of 3-10 (18). It has been found that SP effectively distinguishes between typically developing children and children with various developmental difficulties (19). Turkish adaptation study was done by Kayıhan et al. (20).

Sensory Integration and Praxis Test (SIPT)

The Sensory Integration and Praxis Test (SIPT), developed by Ayres, is a standardized performance-based observational test that evaluates sensory perception and sensory perception-based skills in detail in children between the ages of 4 and 8 years and 11 months (21). SIPT is one of the important gold tests in evaluating sensory development and consists of 17 subtests. These subtests provide information on visuospatial perception, visual discrimination, tactile perception, kinesthesia, following verbal instructions, visual motor planning, imitation of body and mouth movements, balance, bilateral coordination, sequencing of movements, and vestibular processing. There is no Turkish reliability and validity study of this test, which evaluates the child's performance, but it is applied by therapists who have international certification in this regard in our country. On the other hand, some studies have suggested that cultural differences do not affect SIPT

scores (22, 23). In our study, it was decided to use SIPT to compare pre-intervention and post-intervention sensory development scores.

Emotion Regulation Checklist (ERC)

The Emotion Regulation Checklist (ERC) is a 24-item scale developed by Shields and Cicchetti to evaluate the emotion regulation competence of children aged 6-13 and can be evaluated by both parents and teachers (24). The items of the scale evaluate affect lability/negativity and emotion adjustment with the items changing on the plot of "never" and "almost always" on a 4-point Likert scale. Its Turkish adaptation was made by Gül Kapçı et al. (25).

Stroop Test TBAG Form (Stroop TBAG)

The Stroop Test TBAG Form (Stroop TBAG) is one of the golden tests used to measure selective attention and ability to shift attention, focusing on the color used in the spelling of the word and the disruptive effect of the color in the pronunciation of the word (26). The test has cards with color names printed in different colors. The form includes yellow, blue, red and green colors and color names. The dimensions of the form consist of four white cards. On the first card, there are black color names on a white background, on the second card, each color name is different from its own color, on the third card there are circles of different colors, and on the fourth card there are neutral words such as "as much, weak, medium" printed with different colors (27). Stroop test TBAG form is applied in five sections. In the first application part, the words written in black on the first card are required to be read. In the second part, the color names It was requested to read in the area where it was written. In the third part, it is required to say the color names of the circles in different colors, in the fourth part the colors of the neutral words printed in different colors, and in the fifth part, using the card in the second part to be read again. It is one of the important cognitive evaluations that evaluates the child in terms of attention and executive functions, with the brain concentrating on two different situations at the same time (26, 27). Turkish standardization of Stroop TBAG in children aged 6-11 was performed by Kılıç et al. (28).

Childhood Executive Functions Inventory (CHEXI)

Childhood Executive Functions Inventory (CHEXI) is a scale consisting of 26 questions for children aged 4-12 years, developed by Lisa B. Thorell and Lilianne Nyberg as a measurement focusing especially on executive functions (29). CHEXI is divided into 4 subgroups: working memory, planning, inhibition and regulation. Questions are answered by parents or teachers. A

rating from 1 to 5 is made according to the accuracy of the statement in each item. It was translated and adapted into Turkish by Ezgi Kayhan (30).

Participation and Environment Scale for Children and Youth (PEM-CY)

The Participation and Environment Scale for Children and Youth (PEM-CY) is a 28-item questionnaire assessing participation in children aged 5-17 years. It is a family-reported scale that questions the child's participation in school, home and society. It is the first survey to question participation in environmental conditions. In the content of the questionnaire, playing games, participating in artistic activities, watching television, school activities, social interaction and participation in household chores are evaluated (31). Turkish validity, reliability and psychometric properties were studied by Kaya Kara et al. (32).

Conners Teacher Rating Scale (CTRS) and Conners Parent Rating Scale (CPRS)

Conners Teacher Rating Scale (CTRS) and Conners Parent Rating Scale (CPRS) are important behavioral screening and diagnostic scales that have a wide range between the ages of 3-17 and are used quite frequently especially in ADHD (33). CTRS consists of 28 items developed to grade students' classroom behaviors by their teachers (34). The normative data of the Turkish translation of the CTRS were obtained, and its validity and reliability were studied (35). CPRS, on the other hand, is a family-reported scale consisting of a total of 48 items, the Turkish adaptation of which was made by Dereboy et al. The questions in the scale are answered by the parents on a 4-point Likert scale (36).

Bruininks-Oseretsky Motor Proficiency Test-2 (BOT-2)

Bruininks-Oseretsky Motor Proficiency Test-2 (BOT-2) is a test developed for children aged 4-21 and developed to measure the motor functions of children. BOT-2 is an observational assessment evaluating motor performance, consisting of 8 subtests and 12 items in total. It consists of fine motor accuracy, fine motor integration, dexterity, bilateral coordination, balance, upper extremity coordination, endurance, speed and agility subtests (37). The Turkish validity and reliability study of the test was performed by Köse et al. (38).

Goal Attainment Scale (GAS)

The Goal Attainment Scale (GAS) is used to evaluate the achievement of functional therapy goals in children receiving treatment in pediatric services. It helps to set priorities and clear goals for

intervention. It provides the child's continuous interest in the set goals and offers a person-centered approach (39). The determined goals should be specific, measurable, achievable, relevant and well-timed (40). While applying GAS, goals are set for the child and possible outcomes are defined for each goal. After a certain intervention, the functional status of the child is determined again. GAS consists of 5 points as -2, -1, 0, +1 and +2. A score of -2 indicates the child's pre-intervention baseline level, a score of -1 indicates a development below the expected attainment level, a score of 0 indicates an expected attainment level, a score of +1 indicates a better-than-expected achievement, and a score of +2 indicates that the child performs much better than expected (39, 40).

4.7. Collection of Data:

The data will be collected by the occupational therapist from the volunteer participants by face-to-face interview method, and consent and evaluation forms will be collected.

4.8. Intervention Program:

Individuals will be interviewed for the Informed Consent Form. Consent will be obtained from each individual who volunteers to participate in the study. Consent forms will be given in writing and will be requested back once signed.

Participants signing the Informed Consent Form will form the working group, taking into account the inclusion and exclusion criteria. This study group will be divided into two as training and control groups by simple randomization method. After the training and control groups are determined as a result of randomization, an initial evaluation will be made for all participants separately. Ayres Sensory Integration Therapy will be applied to the training group for 10 weeks, 3 days a week (30 sessions), 60 minutes per session. Final assessments will be made at week 11 of therapy. In the control group; An appointment will be made 10 weeks after the initial assessment. After 10 weeks, final evaluations will be made for control. After the final evaluation, 30 sessions of Ayres Sensory Integration Therapy will be applied for 10 weeks, 3 days a week, similar to the control group. In the Ayres Sensory Integration Therapy application, the therapist will provide interviews with the child and their parents in structured environments, and the parents will be asked to repeat the session by explaining the goals in an explanatory way after the session.

Ayres Sensory Integration Therapy will be administered in accordance with the Ayres Sensory Integration Fidelity Measure (ASI-FM). ASI-FM is a manual protocol based on Ayres Sensory

Integration principles (41). This protocol is applied by certified therapists. Researcher [name] has this certificate, it is attached to the end of the file. In addition, a table related to ASI-FM is given below as an example.

Provide sensory opportunities	Presents the child with opportunities for various sensory experiences, which include tactile, vestibular, and/or proprioceptive experiences; intervention involves more than one sensory modality.
Provide just-right challenges	Tailors activities so as to present challenges to the child that are neither too difficult nor too easy, to evoke the child's adaptive responses to sensory and praxis challenges.
Collaborate on activity choice	Treats the child as an active collaborator in the therapy process, allowing the child to actively exert some control over activity choice; does not predetermine a schedule of activities independently of the child.
Guide self-organization	Supports and guides the child's self-organization of behavior to make choices and plan own behavior to the extent the child is capable; encourages the child to initiate and develop ideas and plans for activities.
Support optimal arousal	Ensures that the therapy situation is conducive to attaining or sustaining the child's optimal level of arousal by making changes to environment or activity to support the child's attention, engagement, and comfort.
Create play context	Creates a context of play by building on the child's intrinsic motivation and enjoyment of activities; facilitates or expands on social, motor, imaginative, or object play.
Maximize child's success	Presents or modifies activities so that the child can experience success in doing part or all of an activity that involves a response to a challenge.
Ensure physical safety	Ensures that the child is physically safe either through placement of protective and therapeutic equipment or through the therapist's physical proximity and actions.
Arrange room to engage child	Arranges the room and equipment in the room to motivate the child to choose and engage in an activity.
Foster therapeutic alliance	Respects the child's emotions, conveys positive regard toward the child, seems to connect with the child, and creates a climate of trust and emotional safety.

5. Statistical Analysis of Data:

[figure not shown]
As descriptive statistics in the study; Frequency (n) and percentage (%) values will be used in the evaluation of categorical variables. Shapiro-Wilk and Kolmogorov-Smirnov normality tests will be used for the conformity of numerical variables to the normal distribution, and as descriptive statistics; Mean±standard deviation values will be given for the variables suitable for normal distribution, and median (minimum-maximum) values will be given for those that do not comply with the normal distribution. The appropriate hypothesis testing method planned to be used in the study was determined as "Two-Way Analysis of Variance with Repetitions on a Single Factor" when parametric test assumptions were met. If the parametric test assumptions for the relevant test are not met, whether there is a difference between the groups in terms of quantitative variables, with the "Student t test" when the parametric test assumptions are met, and with the "Mann-Whitney test" if they are not; In examining whether quantitative variables change according to three separate evaluation times, "Repeated measures variance analysis" will be used when the test assumptions are met, and "Friedman test" if it is not provided. Type I error probability will be taken as $\alpha=0.05$ in all hypothesis tests and SPSS v25.0 package program will be used for statistical evaluations. While calculating the sample size required to test the research hypothesis, the effect widths defined by Cohen* were used and the calculations were made with the G*Power 3.1.9 program.

The minimum sample size required for the study is 90 people in total, approximately equally distributed in the groups that will provide 90% test power at 95% confidence level, with the effect width $f=0.30^*$ for "Two-Way Analysis of Variance in Repeated Measurements with Repetitions on a Single Factor".

F tests - ANOVA: Repeated measures, between factors

Analysis: A priori: Compute required sample size

Input:	Effect size f	=	0,3
	α err prob	=	0,05
	Power ($1-\beta$ err prob)	=	0,9
	Number of groups	=	2
	Number of measurements	=	2
	Corr among rep measures	=	0,5
Output:	Noncentrality parameter λ	=	10,8000000
	Critical F	=	3,9493210
	Numerator df	=	1,0000000
	Denominator df	=	88,0000000
	Total sample size	=	90
	Actual power	=	0,9015268

6. Bibliography

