The evaluations to be made within the scope of the study do not involve any risk. At every moment of Ayres Sensory Integration Therapy applications, there will be at least one researcher, including our volunteer child and their parents. Considering all this information, participation in our study does not pose a risk. Difficulty with sensory and motor skills is a common problem for children with attention deficit hyperactivity disorder. With a structured sensory integration therapy application, it is aimed to reduce the sensory, motor and cognitive difficulties of children in their daily lives.

4. Materials and Methods

4.1. Study Place:

In this research, PhD student [name], [name] [name], [name]. [name] and [name]. [name] will take part in the evaluation, data analysis and writing stages. The research will take place in the pediatric rehabilitation unit of Hacettepe University, Department of Occupational Therapy.

4.2. Time to Study:

The study is planned to be completed between February 2023 and April 2024, starting immediately after the approval of the ethics committee.

4.3. Study Population, Sample, Research Group:

Study group and control group will be compared in the research. The change between the last evaluation and the first evaluation will be calculated and a comparison of this change between the two groups will be made. T-test will be used in independent groups for this comparison. The effect size was predicted to be 0.8. With 5% margin of error and 80% power, the sample size was calculated as (45 + 45) 90 for the groups. Participants will be divided into two groups as training group and control group. All volunteering children will be included in the study, taking into account the inclusion and exclusion criteria.

Inclusion criteria:

- a. To be in the age range of 6-8,
- b. Being diagnosed with Attention Deficit Hyperactivity Disorder according to the DSM-V criteria,
- c. Continuing school education,
- d. Having agreed to participate in the study after being informed about the research.

Exclusion criteria:

Children with additional physical and neurological problems will be excluded from the study.

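### Section 4.8 randomises before the initial evaluation and no supplied text says when families learn their group: an avoidable risk to the parent-rated baselines, cheap to remove

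*Combined protocol and SAP*

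**What the plan says.** **Order of steps.** Section 4.8 runs from consent, to division into training and control groups, to baseline: "After the training and control groups are determined as a result of randomization, an initial evaluation will be made for all participants separately". Therapy for the training group, and the control group's appointment 10 weeks later, come after that evaluation.

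**Use of baseline.** Section 4.3 states: "The change between the last evaluation and the first evaluation will be calculated". It then compares this change between the two groups with a t-test.

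**Blinding.** The only statement is in section 4.5 and is garbled, with names removed: "The first and second evaluations were blinded by". Section 4.7 has an occupational therapist collect the data face to face, without saying whether this is the blinded evaluator or the treating therapist.

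**Who rates (section 4.6).**
- Sensory Profile: "The Sensory Profile (SP) is a family-reported scale".
- PEM-CY: "It is a family-reported scale that questions" the child's participation.
- CPRS: "CPRS, on the other hand, is a family-reported scale consisting of a total of 48 items".
- ERC: it "can be evaluated by both parents and teachers".
- CHEXI: "Questions are answered by parents or teachers".

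Three instruments are thus parent-rated, and two more may be.

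**The concern.** Randomisation makes the groups comparable at baseline, apart from chance, only if baseline is measured without knowledge of the group. A blinded evaluator does not blind a parent who fills in a scale. The two groups also face different prospects: 30 sessions starting now, or a 10-week wait with therapy afterwards. A parent who knows which applies might describe the child differently.

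With final ratings held fixed, a group difference in baseline reporting passes in full into the difference in change, and so into a group-by-time interaction. It could create an apparent benefit or hide a real one. The concern covers parent ratings only. It does not extend to the assessor-administered tests (SIPT, BOT-2, Stroop) or to the teacher-rated CTRS.

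**Working it through.** **1. The plan's own figure.** Section 5 gives f = 0.30, α = 0.05, 2 groups, 2 measurements and correlation 0.5 for the between-groups factor. Noncentrality λ = f²·N·m / (1 + (m − 1)ρ) = 0.09 × 90 × 2 / 1.5 = 10.8. The critical F on (1, 88) df is 3.9493 and power is 0.9015. This matches the printed output. N = 90 and ρ = 0.5 are carried forward.

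**2. Inputs to the illustration.**
- From the plan: 45 per arm (section 4.3), α = 0.05 and ρ = 0.5 (section 5), change score compared by t-test (section 4.3).
- Assumed: two-sided test, no true effect, a shift of b SD in one group's baseline ratings, and **no shift in the final ratings**. The documents give no source for b.

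**3. Formulae.** SD of change = √(2(1 − ρ)) outcome SDs, which is 1.0000 at ρ = 0.5. Noncentrality = (b / SD of change) × √(45/2) = (b / SD of change) × 4.7434. The test has 88 df and critical t = 1.9873.

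**4. Results for the change score.** The range shows how far the answer depends on the correlation.

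| Baseline shift b | Noncentrality, ρ = 0.5 | False-positive rate, ρ = 0.5 | Range, ρ = 0.3 to 0.7 |
|---|---|---|---|
| 0.05 SD | 0.2372 | 5.6% | 5.5% to 6.1% |
| 0.1 SD | 0.4743 | 7.6% | 6.8% to 9.3% |
| 0.2 SD | 0.9487 | 15.5% | 12.5% to 22.8% |
| 0.3 SD | 1.4230 | 29.1% | 22.1% to 44.3% |

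**5. What the no-final-shift assumption does.** The bias in the change contrast is (final shift − baseline shift). For a 0.2 SD awareness shift at ρ = 0.5:
- baseline only: 0 − 0.2 = −0.2 SD, rate 15.5%;
- equal at both times: 0.2 − 0.2 = 0, rate 5%;
- final only: 0.2 − 0 = +0.2 SD, rate 15.5% with opposite sign.

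**6. The test used for sample size.** In a group main effect averaged over two measurements, a baseline shift of b contributes b/2, and the SD of the mean is √((1 + ρ)/2). For b = 0.2 and ρ = 0.5 the noncentrality is (0.1 / 0.8660) × 4.7434 = 0.5477, giving 8.4%. Over ρ = 0.3 to 0.7 the rate is 9.0% to 8.0%.

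**The case against.** **Determined is not disclosed.** Nothing supplied says that families are told before baseline. The consent pages and some other parts of the file were not available, and a consent form could cover the timing. This stands, and it limits the point to a risk. Section 4.8 is nonetheless where the sequence is set out, and it states no safeguard.

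**The first evaluation is described as blinded.** This shows an intention to protect baseline. The sentence is too garbled to say for certain who is blinded. The evaluator is the likeliest reading, and on that reading parents are not covered.

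**Families know their group by the final evaluation anyway.** This is the strongest objection. If knowing the group shifts parent ratings equally at both times, the shift cancels in the change score. Protecting only the baseline would then leave the final shift exposed. So the table in the working shows one scenario and is not the benefit of the fix, whose net effect on a change-score error rate is unknown. The reorder is still sound: it restores a baseline that allocation cannot influence, and it does not rely on two biases happening to offset each other.

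**A stronger reading.** A reader might infer that the parent-rated baselines are biased, or that the trial's false-positive rate is 15% or more. The documents support neither: the disclosure time is not stated and the shift sizes are assumptions. In addition, no primary outcome is named in the supplied text, so how far the main conclusion rests on parent scales is unknown.

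**Conclusion.** The point holds as an avoidable risk to the parent-rated baselines: the stated order permits families to know their group when they rate, and no supplied text prevents it. It is not a shown bias, and its direction and size are unknown.

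The 7.6%, 15.5% and 29.1% figures depend on families knowing the group at baseline, on assumed shifts of 0.1, 0.2 and 0.3 SD, on ρ = 0.5, on no true effect and on unshifted final ratings. A shift of 0.05 SD or less matters little, and the group main effect is much less affected than the change score. The change is worth making because it costs almost nothing. It is a cheap improvement, not a defect that undermines the design.

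**What to change.** In section 4.8, set the order as consent, eligibility, completed initial evaluation including the parent-rated forms, then randomisation and disclosure of the group. At minimum, add a sentence that the allocation is withheld from families until the parent baseline forms are complete. Teacher forms need not delay allocation.

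If children are already enrolled under the present order, record and report for each child the date of disclosure and the date of the baseline forms. In either case, report the final parent ratings as unblinded and interpret them with that limit, because the reorder protects the baseline only.

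**Cost.** A short text change, with N unchanged at 90. The group is known slightly later. The steps in section 4.8 that depend on the group, the start of therapy and the control appointment, already follow the initial evaluation.

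### The final evaluation is timed from therapy in the training arm and from the initial assessment in the control arm, so change-score intervals can differ, and evaluation of training children who never start or stop is not specified

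*Combined protocol and SAP*

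**What the plan says.** Section 4.3 defines the quantity to be analysed: "The change between the last evaluation and the first evaluation will be calculated", and this change is compared between the two groups.

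Section 4.8 sets the timetable:

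- **Baseline, both arms.** After randomization, "an initial evaluation will be made for all participants separately".
- **Training arm.** "Ayres Sensory Integration Therapy will be applied to the training group for 10 weeks, 3 days a week (30 sessions), 60 minutes per session". Then: "Final assessments will be made at week 11 of therapy".
- **Control arm.** "An appointment will be made 10 weeks after the initial assessment", and "After 10 weeks, final evaluations will be made for control". The control children are offered the same 30 sessions only after that evaluation.

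Section 4.8 does not state how soon after the initial evaluation the first session takes place, what visit window applies, whether missed sessions push the final evaluation back, or whether a child who stops therapy is still evaluated. Section 5 names no analysis set and no method for missing data.

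**The concern.** A difference in change scores estimates the effect of therapy only if both arms have had the same time in which to change. Here the control clock starts at the initial assessment and the training clock starts with therapy. Any wait before the first session lengthens the training interval and leaves the control interval alone. Children aged 6 to 8 can be expected to improve with age on at least some performance measures, so on those measures extra weeks would be counted as treatment effect.

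The second issue does not depend on any growth rate. A control child's final date can be fixed on the day of the initial assessment, whatever happens later. A training child's date is defined by therapy. If the rule were applied so that only children still in therapy are evaluated, a selected training group would be compared with an unselected control group, and the protection of randomization would be lost.

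**Working it through.** **1. Interval in each arm.** Let g be the number of weeks from initial evaluation to first session (not given in the documents). Week 11 begins once 10 weeks are complete and ends at 11 weeks.

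- Training interval: g + 10 to g + 11 weeks.
- Control interval: 10 weeks.
- Planned excess in training: g to g + 1 weeks.

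| g (assumed) | Training interval (weeks) | Control (weeks) | Excess (weeks) |
|---|---|---|---|
| 0 | 10–11 | 10 | 0–1 |
| 1 | 11–12 | 10 | 1–2 |
| 2 | 12–13 | 10 | 2–3 |
| 4 | 14–15 | 10 | 4–5 |

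If week 11 is counted by sessions delivered rather than by the calendar, missed sessions lengthen the training interval further.

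**2. Size of the resulting bias.** The documents give no growth rate. Assume 0.5 to 1.0 SD per year on raw scores. Bias = growth per year × extra weeks / 52.

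- 1 week: 0.5/52 = 0.010 to 1.0/52 = 0.019 SD.
- 4 weeks: 0.5 × 4/52 = 0.038 to 1.0 × 4/52 = 0.077 SD.

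Section 4.3 predicts an effect size of 0.8 for the change comparison. Against that, 4 extra weeks are 0.038/0.8 = 5% to 0.077/0.8 = 10%. This uses one SD for raw and change scores, which agrees with the correlation of 0.5 entered in section 5: SD of change = SD × √(2 × (1 − 0.5)) = SD.

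**3. Effect on false positives.** With 45 per arm, a two-sided t-test at 0.05 and no true treatment effect, the rejection rate is 5.0% at a bias of 0.01 SD, 5.6% at 0.05 SD and 7.6% at 0.10 SD. The one-week bias (at most 0.019 SD) therefore stays below 5.6%, and the 4-week bias (at most 0.077 SD) below 7.6%.

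**4. Is a start delay credible?** Both arms are to receive 30 one-hour sessions: 90 × 30 = 2,700 hours. February 2023 to April 2024 is about 65 weeks, so 2,700/65 = 41.5 hours per week. Sections 4.5 and 4.8 appear to point to one certified therapist. The training arm alone needs 45 × 30 = 1,350 hours, or 1,350/65 = 20.8 hours per week. The total makes some delay credible. It does not give its length, which depends on how entry is staggered.

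**5. Children who stop.** If 20% of the training arm were not evaluated (an assumption), the t-test at effect size 0.8 would keep power of 0.942 with 36 and 45 children, against 0.964 with 45 and 45. Loss of precision is minor; the problem is selective loss in one arm.

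**6. The plan's own sample size.** Section 5 uses f = 0.3, N = 90, 2 measurements and correlation 0.5: λ = 0.3² × 90 × 2/(1 + 0.5) = 10.80. With 1 and 88 degrees of freedom and critical F 3.949, power is 0.9015, as printed. The evaluation interval does not enter, so aligning the clocks leaves this figure unchanged.

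**The case against.** The strongest reply is that the two rules describe the same moment. Therapy lasts 10 weeks, week 11 opens when 10 weeks are complete, and the control evaluation also falls at 10 weeks. With a prompt start and no slippage the intervals can be identical. That stands: a reader might infer that the change scores necessarily cover different intervals, and the documents do not support it. They show different anchors and no rule that keeps the intervals aligned.

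Other stronger readings also fail:

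- **That a child who stops can have no final evaluation.** If week 11 is a calendar week from the first session, a child who started and then stopped still has a date; only a child who never started has none. The text does not say that either would be evaluated, but nor does it restrict the training arm to completers.
- **That the workload proves a wait of several weeks.** Half of the 2,700 hours falls after the control children's final evaluation, no waiting time is stated, and the weekly capacity and number of therapists are not given.
- **That the bias always favours therapy.** Many outcomes are parent or teacher ratings, and the Goal Attainment Scale is scored against individual goals. The documents show no age trend or direction for these.

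What remains is that the timing rule differs by arm, can err in one direction only, and leaves evaluation after stopping unspecified.

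**Conclusion.** The concern holds in a limited form. Section 4.8 uses different time anchors in the two arms for an outcome defined as change between two evaluations. The planned excess in the training arm is the unstated start delay plus 0 to 1 week, never negative.

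With a prompt start the bias is negligible. It becomes worth preventing with delay, but even an assumed 4 weeks adds less than 0.08 SD. Those sizes rest on an assumed growth of 0.5 to 1.0 SD per year and apply only to measures that improve with age.

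The silence on training children who never start or who stop is the weightier half, because it bears on whether the randomized groups are compared as randomized. Its size cannot be computed, since the plan gives no expected rate of stopping. The plan should be changed because the remedy is cheap, not because a large bias has been shown.

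**What to change.** Replace the two timing rules in section 4.8 with one, for example:

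> In both arms the final evaluation is done at the same number of weeks after the initial evaluation, within the same window (for example ± 1 week), for every randomized child whatever the number of sessions attended; the actual interval is recorded.

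If the initial evaluation is to be scheduled around available therapy slots, the same scheduling must apply to both arms, for example by evaluating training and control children of the same randomization block together. Randomization precedes the initial evaluation, so holding back only the training children would move the arm difference to before baseline rather than remove it.

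The cost is a short change to the text and some appointment planning. The downside is that a training child who starts late may be evaluated before completing all sessions; the recorded interval and number of sessions attended would make this visible. The sample size of 90 and the stated power of 0.9015 are not affected.
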